9.1.3. Sensitivity Analyses of the Primary Analysis

The following sensitivity analyses may be performed:

9.1.3.1. Missing at Random Multiple Imputation

For this imputation approach, all values will be imputed under the assumption that they are missing at random. A staged approach as described in section 9.1.1 will be used to first impute sporadic missing values with MCMC, then a monotone regression approach for the second stage. However, all patients will have missing values imputed within treatment group under the MAR assumption.

9.1.3.2. Missing Not at Random Multiple Imputation: All patients imputed from the placebo distribution

For this imputation approach, a staged approach as described in section 9.1.1 will be used to first impute sporadic missing values with MCMC, then a monotone regression approach for the second stage. However, all patients will have missing values imputed using the placebo distribution as reference. This will inform the hypothetical possibility that all subjects revert to the placebo distribution regardless of their reason for dropout.

Statistical Analysis Plan: TNX-TI-M201

9.1.3.3. Multiple Imputation Tipping Point

A tipping point analysis will be performed using the primary analysis MI datasets (from section 9.1.2) and applying an increasing delta (of MADRS score) to the active group until statistical significance is no longer achieved. The delta will only be applied to imputed values; this will be done in 0.5 increments on the MADRS total score. This will only be performed if the primary analysis is significant. This will test the overall robustness of the primary analysis.

9.1.3.4. Current MADRS Version

The first sixteen subjects were inadvertently assessed under an older version of the MADRS (see Clinical Information Amendment dated 25Sep2023 and referenced in section 2). To assess the impact of this, the primary analysis will be repeated with these 16 subjects excluded.

9.1.4. Secondary Analyses of the Primary Endpoint

In addition to the change from baseline to Week 6 in the MADRS total score, the change from baseline at Week 2 and Week 4 will also be reported out of the primary MMRM model described in section 9.1.2.

Additionally, three responder-type analyses of the MADRS total score will be performed:

- Proportion of patients achieving response, defined as a ≥50% decrease from Baseline (Visit 2) in MADRS total score, assessed at Weeks 2, 4, and 6
- Proportion of patients in remission, defined as a MADRS total score <=10, assessed at Weeks 2,4, and 6
- Proportion of patients achieving sustained response, defined as a ≥50% decrease from Baseline (Visit 2) in MADRS total score at Weeks 4 and 6

For each, the number and percentage of responders (with response for each as described above) and non-responders will be reported, with missing values considered non-responders. 95% CIs of the percentages will be given, as well as the difference between treatment groups in percentages, its 95% Wald CI, and p-value comparing the groups. Groups will be tested using a difference in proportions Z test (equivalent to a Pearson's Chi-Squared). In the case of low cell counts (<5 expected in a given cell), then Fisher's exact test will be used instead.

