7.3.3. Exploratory Efficacy Endpoints

- Proportion of patients achieving response, defined as a ≥50% decrease from Baseline (Visit 2) in MADRS total score, assessed at Weeks 2, 4, and 6
- Proportion of patients in remission, defined as a MADRS total score ≤10 at Weeks 2, 4, and
 6
- Proportion of patients achieving sustained response, defined as a ≥50% decrease from Baseline (Visit 2) in MADRS total score at both Weeks 4 and 6
- Proportion of patients with a Clinician Global Impression Improvement Scale (CGI-I) rating of "very much improved" or "much improved" at Weeks 2, 4, and 6
- Mean CGI-I score at Weeks 2, 4, and 6
- Change from Baseline (Visit 2) in Patient Global Impression of Severity Scale (PGIS) score at Weeks 2, 4, and 6
- Proportion of patients with a Patient Global Impression of Change (PGIC) rating of "very much improved" or "much improved" at Weeks 2, 4, and 6
- Mean PGIC score at Weeks 2, 4, and 6
- Change from Baseline (Visit 2) to Week 6 in the CSFQ-14 total score in females and in males (analyzed separately)
- Change from Baseline (Visit 2) in the MADRS total score at Week 2 and Week 4

Version 2.0, 02 March 2023

- Change from Baseline (Visit 2) in the CGI-S score at Week 2 and Week 4
- Change from Baseline in the SDS total score at Week 2 and Week 4
- Change from Baseline (Visit 2) in the Hamilton Anxiety Rating Scale (HARS) total score at Weeks 2, 4, and 6
- Change from Baseline (Visit 2) in each of the 3 domains (work/school; social life; home life or family responsibilities) using the SDS at Weeks 2, 4, and 6
- Proportion of patients with a CGI-S rating of "normal, not at all ill" or "borderline mentally ill" at Weeks 2, 4, and 6
- Proportion of patients with a PGIS rating of "not present", "very mild", or "mild" at Weeks 2, 4, and 6

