9. ENDPOINT EVALUATION

9.1. Primary Endpoint

[figure not shown]
The primary efficacy endpoint will be the change from baseline in the MADRS total score at Week 6.

The MADRS is a validated, 10-item, clinician-administered depression scale. It will be completed at Screening (Visit 1), Baseline (Visit 2) and after Weeks 2, 4, and 6 of treatment (Visits 3, 4, and 5, respectively). The 10 items measure the core symptoms and cognitive features of clinical depression. This scale has historically been used in drug treatment trials due to its particular sensitivity to detect treatment effects.

Patients with a Screening (Visit 1) MADRS score of $\geq 28, \geq 25$ at Baseline (Visit 2), and a $\leq 25\%$ decrease or increase in MADRS score from Screening (Visit 1) to Baseline (Visit 2) are eligible to be randomized.

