9.1.2. Primary Analysis of the Primary Endpoint

Summary statistics (mean, SD, median, minimum, maximum) for the primary efficacy endpoint will be reported for the change from the Baseline to week 6 for each of the treatment groups. The change from Baseline will be analyzed in an MMRM model for each multiple imputation set with fixed effects of treatment, visit, baseline value, treatment by visit interaction, baseline by visit interaction and pooled site; an unstructured covariance matrix will be used. Sites with less than 5 patients will be pooled into a single site; this covariate may be removed from the model in the case of convergence issues. Least square means (LSMs), standard errors, and the LSM differences (treatment vs placebo) for each of the 20 MI repeats will be combined using SAS procedure MIANALYZE (Rubin, 1976) and 95% CIs and p-values will be reported for each. Denominator degrees of freedom will use the Kenward Rogers approach. Should the model with unstructured variance fail to converge using the default Newton-Raphson approach, the Fisher scores (via the SCORING option of the PROC MIXED statement) will be utilized. Should this also fail to converge, then other approaches as detailed in Lu 2010 will be utilized. Once these approaches have been exhausted, then the following structures will be used in order with the first to converge being selected: heterogeneous Toeplitz, heterogeneous first-order autoregressive, Toeplitz, first order autoregressive and compound symmetric will be attempted in that order; in these cases, the sandwich estimator (Diggle and Kenward 1994) will be used to estimate the standard errors of the fixed effects parameters and the denominator degrees of freedom will utilize the DDFM=BETWITHIN option in SAS®.

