9.2.2. Exploratory Endpoints

9.2.2.1. Continuous Exploratory Endpoints

Each of the following continuous endpoints will be summarized:

- Change from Baseline (Visit 2) in the CGI-S score at Week 2 and Week 4
- Change from Baseline (Visit 2) in the SDS total score at Week 2 and Week 4
- Change from Baseline (Visit 2) in PGIS score at Weeks 2, 4, and 6
- Change from Baseline (Visit 2) to Week 6 in the CSFQ-14 total score in females and in males (analyzed separately)
- Change from Baseline (Visit 2) in the HARS total score at Weeks 2, 4, and 6
- Change from Baseline (Visit 2) in each of the 3 domains (work/school; social life; home life or family responsibilities) using the SDS at Weeks 2, 4, and 6
- Mean PGIC score at Weeks 2, 4, and 6
- Mean CGI-I score at Weeks 2, 4, and 6

The CGI-S score and SDS total score at Week 2 and Week 4 will be reported out of the same MMRM model used for each of these key secondary endpoints.

Statistical Analysis Plan: TNX-TI-M201

The PGIS, HARS total score, and SDS domains (work/school; social life; home life or family responsibilities) will be analyzed using a model identical to the primary efficacy endpoint, but on observed data only, without multiple imputation. Additionally, the primary efficacy and key secondary endpoints will be reported out of an MMRM without imputation.

The CSFQ-14 total score will be summarized with descriptive statistics and compared between groups with an ANCOVA with effects for treatment and baseline value.

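### MADRS remission is compared only by an unadjusted test; a supportive baseline-adjusted risk difference would be slightly more precise

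*SAP*

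**What the plan says.** Protocol 7.3.3 lists remission as an exploratory endpoint ("Proportion of patients in remission, defined as a MADRS total score ≤10"), and SAP 9.1.4 uses the same cut-off ("defined as a MADRS total score <=10"). For each MADRS responder endpoint, SAP 9.1.4 counts missing values as non-response and reports the percentages with "the difference between treatment groups in percentages, its 95% Wald CI, and p-value comparing the groups". The test is unadjusted: "Groups will be tested using a difference in proportions Z test". Fisher's exact test replaces it when counts are sparse: "In the case of low cell counts (<5 expected in a given cell").

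The baseline value is available. SAP 9.1 says of the MADRS: "It will be completed at Screening (Visit 1), Baseline (Visit 2) and after Weeks 2, 4, and 6 of treatment". The SAP also adjusts for baseline elsewhere. The primary MMRM in 9.1.2 is fitted "with fixed effects of treatment, visit, baseline value, treatment by visit interaction, baseline by visit interaction and pooled site", and the exploratory CSFQ-14 total in 9.2.2.1 is "compared between groups with an ANCOVA with effects for treatment and baseline value". Neither document describes an adjusted analysis of remission, and the subgroup analyses in 9.2.2.3 cover only the primary and key secondary endpoints.

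**The concern.** Response and sustained response are defined relative to each patient's own baseline. Remission is not. With entry at a baseline MADRS of 25 or more, a patient at 25 has to fall 15 points to reach 10, and a patient at 40 has to fall 30. If baseline predicts the later score, part of the variation in remission is explained by a value already in the database, and a crude comparison leaves that variation in the standard error.

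What is at stake is the width of one exploratory interval. Protocol 13.4.3 makes the p-value descriptive, so the estimate and its interval are the main product of this analysis, and the interval is what adjustment would narrow. No confirmatory conclusion is affected.

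**Working it through.** **Inputs from the documents.** About 300 patients, 1:1, so 150 per arm (SAP 7.2 and 8.1.6); baseline MADRS at least 25 (protocol 8.4); remission at 10 or less; missing counted as non-remission (SAP 9.1.4). The plan gives no precision or power figure for remission, so there is none to reproduce.

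**Assumed inputs.** Baseline MADRS mean 32.0 and SD 4.2, truncated at 25; Week 6 SD 10; treatment effect 3.3 points; 12% missing; remission, with missing counted as failure, of 15% on placebo and 23% on active, or 24% and 35%.

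**Step 1: crude precision.** SE = sqrt[p0(1−p0)/150 + p1(1−p1)/150].

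- 15% and 23%: sqrt(0.1275/150 + 0.1771/150) = 0.0451; half-width 1.96 × 0.0451 = 8.8 points.
- 24% and 35%: sqrt(0.1824/150 + 0.2275/150) = 0.0523; half-width 1.96 × 0.0523 = 10.2 points.

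**Step 2: adjusted estimate.** Fit logit P(remission) = b0 + b1·treatment + b2·baseline MADRS. For each patient, predict the probability under active and under placebo, then average the difference over all patients. The SE comes from the influence function with an n−3 correction. The pooled Z test, the unpooled Wald interval and this estimator were run on the same simulated trials, 20,000 per scenario.

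The correlation is that of baseline with Week 6 MADRS; slope = correlation × 10 / baseline SD (small differences come from rounding the SD to 4.2). In the proportional case, improvement is proportional to baseline, so slope = placebo Week 6 mean / 32.0: 20.0/32.0 = 0.63 or 16.5/32.0 = 0.52.

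| Correlation | Slope | SE change vs unpooled crude | Half-width narrower by (points) | Equivalent extra patients | Power added by baseline (points) |
|---|---|---|---|---|---|
| 0.1 | – | 0.1% larger | none | none | – |
| 0.2 | 0.47 | 0.5–0.6% smaller | 0.04–0.06 | 3–4 | 0.2–0.5 |
| 0.22–0.27 (proportional) | 0.52–0.63 | 0.8–1.1% smaller | 0.07–0.11 | 5–7 | 0.6–0.9 |
| 0.3 | 0.71 | 1.5–1.8% smaller | 0.13–0.18 | 9–11 | 1.3 |
| 0.4 | 0.94 | 2.9–3.4% smaller | 0.25–0.35 | 18–22 | 2.1–3.2 |

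With g the proportional SE reduction, the narrowing is half-width × g; at 0.3, 8.8 × 0.015 = 0.13 and 10.2 × 0.018 = 0.18. The patient equivalent is 300 × [1/(1−g)² − 1]; at 0.3, 300 × (1/0.985² − 1) = 9.2 and 300 × (1/0.982² − 1) = 11.1.

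The planned pooled Z test has power of 47–52% in these scenarios. Moving from a pooled to an unpooled SE adds 0.4–0.6 points by itself. The last column excludes that (Monte Carlo SE 0.14–0.21 points).

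**Step 3: wider inputs.** With placebo remission 10–30%, missing 5–20% and Week 6 SD 9–12 (8,000 trials each), the SE is 0.3–0.8% smaller at correlation 0.2 and 2.1–4.1% smaller at 0.4. Baseline adds −0.5 to +1.0 and +1.4 to +3.6 power points respectively.

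**Step 4: a second simulation with other assumptions.** It used baseline SD 3.6 or 4.8, residual SD 9.5, a 3-point effect, 15% missing, and placebo remission of 15% or 30% before missing data (1,500 trials each). The crude-to-adjusted variance ratio was about 1.00 at correlations up to 0.11, 1.01–1.03 at 0.15–0.25, 1.03–1.04 at 0.29 and 1.04–1.10 at 0.35–0.45. Mean crude and adjusted risk differences agreed within 0.001, so the estimand does not change.

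**Step 5: validity and sparse weeks.** In the Step 2 scenarios under the null, the adjusted test rejected in 4.9–5.4% of trials and the pooled Z test in 4.9–5.3%. With 150 per arm, the expected number of remitters per arm is half the total, so the Fisher rule triggers when there are fewer than 10 remitters. The logistic fit failed in 9–10% of trials at a 2% remission rate and in about 2% at 3%. Across rates of 1.5–8%, at most 0.08% of trials had a failed fit without also triggering the Fisher rule. Where the rule was not triggered, at rates of 3–8%, the adjusted test's type I error was 4.5–6.6%.

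**The case against.** The strongest reply is that nothing here is broken and the payoff is negligible. Remission is exploratory, and extra power on a descriptive p-value supports no decision. In the proportional case the interval narrows by only 0.07–0.11 points on 8.8–10.2. The larger gains need a correlation of 0.4, which implies a slope of 0.94 against 0.52–0.63 in the proportional case, and the entry criteria restrict the baseline range, which tends to weaken the correlation. An absolute cut-off does not by itself make remission depend on baseline; baseline must also predict the later score, and the documents do not say how well it does. At early visits with few remitters there is less to gain: at rates of 3–8% and a correlation of 0.25, the SE falls 0.25–0.5%, or about 0.01–0.03 points. The CGI-S and PGIS categories in SAP 9.2.2.2 are also absolute cut-offs with a Visit 2 value and would stay unadjusted, and the primary MMRM already gives baseline-adjusted MADRS results at all three weeks.

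All of this is correct as to size, and it is why the point is optional. It does not show that the adjustment is wrong or harmful: the estimand is unchanged and the crude analysis stays. The SAP would allow an adjusted estimate later, but under sections 2 and 8.1.4 it would be labelled post hoc. Writing it in now avoids that.

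**Conclusion.** The point holds as a minor, optional improvement. The only planned comparison of remission ignores a baseline value that is collected and used elsewhere in the SAP. Using it would reduce the standard error by roughly 0.5% to 3.4% for correlations of 0.2 to 0.4, and by nothing at 0.1. These sizes rest entirely on assumed SDs, remission rates, missingness and correlations, and the correlation matters most. The planned Z test and Wald interval remain valid, and no primary or key secondary conclusion changes.

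**What to change.** In SAP 9.1.4, keep the crude percentages, Wald interval and Z or Fisher test as the simple summary. For remission at Weeks 2, 4 and 6, add as a supportive estimate a risk difference with 95% CI, standardised over baseline MADRS (g-computation) from a logistic model with treatment and baseline MADRS. Name one influence-function (robust) standard error in advance, and continue to count missing values as non-remission. Report the estimate only where no expected cell count is below 5, so that the existing Fisher rule also covers sparse weeks. No site term is needed, and no change is asked for response, sustained response or the other responder endpoints.

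The cost is one or two sentences, minor programming and up to three extra estimates in the tables. If baseline and Week 6 MADRS turn out to be weakly correlated, the added interval will be almost identical to the crude one.

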9.2. Secondary Endpoints

All secondary efficacy analyses will be based on the ITT population.

9.2.1. Key Secondary Endpoints

There will be two key secondary endpoints:

9.2.1.1. Change from Baseline (Visit 2) in the CGI-S score at Week 6

The CGI-S score will be scored 1-7 and treated as a continuous variable. It will be analyzed in a manner identical to the primary endpoint (MMRM with MI using an MNAR approach for patients dropping for AEs and LOE).

Sensitivity analyses will include considering all patient dropouts as missing at random (paralleling the approach in section 9.1.3.1) and considering all patient dropouts as missing not at random (paralleling the approach in section 9.1.3.2).

9.2.1.2. Change from Baseline (Visit 2) in the SDS total score at Week 6

For participants that respond to all three questions (work, social life/leisure and home) on the SDS, their total score will be the sum of the three items. Participants that do not respond to the work/school item because they have not worked or attended school in the recall period for reasons unrelated to their disease state will not have that value imputed; to retain the 0 to 30 scaling for the total score, the participant's other two items will be summed and multiplied by 1.5. This approach reports the disease impact on the applicable domains. Due to the design of the ePRO, participants may both respond to the work/school item and check the box that they have not worked or attended school in the recall period for reasons unrelated to their disease state. In these instances, the checkbox will supersede the response and the 0-10 score will be censored; as above, the participant's other two items will be summed and multiplied by 1.5. Participants that have either of the other items missing or have work/school item missing but do not check the box to indicate that they did not work/attend school will be assigned a missing value.

The SDS total score will be analyzed in a manner identical to the primary endpoint (MMRM with MI using an MNAR approach for patients dropping for AEs and LOE).

Sensitivity analyses will include considering all patient dropouts as missing at random (paralleling the approach in section 9.1.3.1) and considering all patient dropouts as missing not at random (paralleling the approach in section 9.1.3.2).

9.2.2. Exploratory Endpoints

9.2.2.1. Continuous Exploratory Endpoints

Each of the following continuous endpoints will be summarized:

- Change from Baseline (Visit 2) in the CGI-S score at Week 2 and Week 4
- Change from Baseline (Visit 2) in the SDS total score at Week 2 and Week 4
- Change from Baseline (Visit 2) in PGIS score at Weeks 2, 4, and 6
- Change from Baseline (Visit 2) to Week 6 in the CSFQ-14 total score in females and in males (analyzed separately)
- Change from Baseline (Visit 2) in the HARS total score at Weeks 2, 4, and 6
- Change from Baseline (Visit 2) in each of the 3 domains (work/school; social life; home life or family responsibilities) using the SDS at Weeks 2, 4, and 6
- Mean PGIC score at Weeks 2, 4, and 6
- Mean CGI-I score at Weeks 2, 4, and 6

The CGI-S score and SDS total score at Week 2 and Week 4 will be reported out of the same MMRM model used for each of these key secondary endpoints.

Statistical Analysis Plan: TNX-TI-M201

The PGIS, HARS total score, and SDS domains (work/school; social life; home life or family responsibilities) will be analyzed using a model identical to the primary efficacy endpoint, but on observed data only, without multiple imputation. Additionally, the primary efficacy and key secondary endpoints will be reported out of an MMRM without imputation.

The CSFQ-14 total score will be summarized with descriptive statistics and compared between groups with an ANCOVA with effects for treatment and baseline value.

The PGIC and the CGI-I will be considered both as responder analyses (see below) and as continuous 1-7 values. For continuous PGIC and the CGI-I, summary statistics (mean, SD, median, minimum, maximum) will be reported for each visit for each of the treatment groups. They will be analyzed in an MMRM model with fixed effects of treatment, visit, treatment by visit interaction, and site; an unstructured covariance matrix will be used. Least square means (LSMs), standard errors, and the LSM differences (each treatment vs placebo) with 95% CIs and p-values will be reported for each visit. Denominator degrees of freedom will use the Kenward Rogers approach. Should the model with unstructured variance fail to converge using the default Newton-Raphson approach, the Fisher scores (via the SCORING option of the PROC MIXED statement) will be utilized. Should this also fail to converge, then other approaches as detailed in Lu 2010 will be utilized. Once these approaches have been exhausted, then the following structures will be used in order with the first to converge being selected: heterogeneous Toeplitz, heterogeneous first-order autoregressive, Toeplitz, first order autoregressive and compound symmetric will be attempted in that order; in these cases, the sandwich estimator (Diggle and Kenward 1994) will be used to estimate the standard errors of the fixed effects parameters and the denominator degrees of freedom will utilize the DDFM=BETWITHIN option in SAS®.

9.2.2.2. Categorical Secondary Endpoints

The following categorical endpoints will be tabulated:

- Proportion of patients with a CGI-I rating of "very much improved" or "much improved" at Weeks 2, 4, and 6
- Proportion of patients with a PGIC rating of "very much improved" or "much improved" at Weeks 2, 4, and 6
- Proportion of patients with a CGI-S rating of "normal, not at all ill" or "borderline mentally ill" at Weeks 2, 4, and 6
- Proportion of patients with a PGIS rating of "not present", "very mild", or "mild" at Weeks 2, 4, and 6

For each, at each visit, the number and percentage of patients in each category (without dichotomizing) will be reported as well as the number of missing values. The number and percentage of responders (with response for each as described above) and non-responders will be reported, with missing values considered non-responders. 95% CIs of the percentages will be given, as well as the difference between treatment groups in percentages, its 95% Wald CI, and p-value comparing the groups. Groups will be tested using a difference in proportions Z test

Statistical Analysis Plan: TNX-TI-M201

(equivalent to a Pearson's Chi-Squared). In the case of low cell counts (<5 expected in a given cell), then Fisher's exact test will be used instead.

